## **1.0 Procedures Involved**

### *1.1 Describe and explain the study design.*

The study uses a quasi-experimental design with a waitlist control. Youth will be recruited and randomly assigned to either the experimental group or the waitlist control group. At the completion of the experimental group, the waitlist control group will start.

### *1.2 Provide a description of all research procedures being performed and when they are performed, including procedures being performed to monitor subjects for safety or minimize risks.*

Students will take pre-tests before participating in an 8-week small group therapy. Afterwards, post-tests will be administered and students will be given a chance to provide feedback. A list of the measures is below.

Recruitment will occur by advertising via social media outlets (e.g., Facebook groups targeting local moms) and through local schools. The graphic in the file titled “participants needed” will be posted on social media.

An online survey will be shared with interested caregivers to gauge eligibility. Caregivers will first provide parental consent for their child’s participation, then an eligibility questionnaire will be administered electronically. To be eligible for the study, their child must 1) be a middle or high school student (via caregiver report), 2) have access to a computer with webcam and a private space for each meeting (via caregiver report), and 3) have experienced at least one instance of peer victimization in the past month. The goal is to enroll 6-7 students in the group. Once the group has been enrolled, student assent will be gathered and pre-test surveys will be administered. Participants completing the intervention will be asked to complete the post-test surveys and will be invited to be part of the focus group to gather their feedback.

### *1.3 Describe:*

- *Procedures performed to lessen the probability or magnitude of risks.*

Participants in IVY may experience distress related to their participation in the program. Clinicians with training and clinical experiences working with adolescents and small groups will co-lead all sessions. If a student becomes too distressed to continue, one group leader can work individually with that participant while the other group leader continues with the lesson. In addition, strategies for dealing with distress are built into the curriculum. These strategies are introduced in the first few sessions so that participants are equipped with coping, relaxation, and self-care techniques before they are asked to reflect on their own victimization experiences. Live coding of treatment fidelity will be used so that group meetings do not have to be video or audio recorded then stored. One dataset that connects names, id numbers, and responses will be stored on a password protected computer. All other data will be identified using a study-specific ID number. For the virtual participants, best practices for telehealth will be followed (cite). A

HIPAA-compliant videoconferencing software will be used. The physical address of the participant and the name and phone number of a safety contact will be verified before each session. An alternate phone number will be gathered in case of technology problems. All participants will have access to resources for crisis counseling should the need arise between sessions. Caregivers will have the ability to contact the PI for non-crisis concerns.

**SURVEYS.** To screen for potential participants, the BESS and victim subscale of the BPBQ will be used. For the eligibility screener, participants will answer 40 items.

- **Victimization.** To assess victimization the victim subscale from the *Bullying Participant Behavior Questionnaire* (BPBQ; Demaray et al., 2014) will be used. This subscale contains 10 items. Participants respond to each item using a Likert scale ranging from 1 (*Never*) to 5 (*7 or more times*) in the past 30 days. The factor structure was supported via exploratory and confirmatory factor analysis. Alpha coefficients for each subscale ranged from .88 to .94 (Demaray et al., 2014). Only scores from the Victim subscale will be used.
- **Social-emotional distress.** The BASC-3 Behavioral and Emotional Screening System (BESS; Kamphaus & Reynolds, 2015) is designed for students in grades 3-12 and consists of 30 items that measure Personal Adjustment, Internalizing Problems, and Self-Regulation. Dever et al. (2020) report evidence for the three-factor structure, as well as strong concurrent validity, predictive validity, and test-retest reliability. For each item, participants decide how often a statement is true for them and respond using a 4-point Likert scale (*Never* to *Always*).

For the study, four measures will be used pre- and post-intervention: the BESS, COPE, FBBA, and SEI. For the study, participants will answer 77 items. All measures are described below.

- **Social-emotional distress.** The BASC-3 BESS (described above; Kamphaus & Reynolds, 2015), which is part of the eligibility screener, will also be used for pre- and post-intervention assessments.
- **Knowledge of Self-protection Skills.** The Knowledge of Self-Protection Options (KSPO) was created by adapting the Forms of Bullying Bystander Actions ([name] et al., under review), which assesses bystander intervention options. The items assess different types of self-protection skills (e.g., direct intervention, protect emotions, and reporting to adults), which will be taught during IVY.
- **Self-efficacy for Protecting Self.** The Self-Efficacy for Protecting Self (SEPS) scale was created for the purpose of this project to measure participants' perceptions that they would be able to protect and defend themselves in future victimization experiences. It was modeled after other self-efficacy for intervention scales (e.g., intervening in bullying [Andreou et al., 2005] and cyberbullying [Bussey et al., 2015]). The SEPS consists of 9 defending options that were drawn from the KSPO (described above). Response options range from 1 (*I cannot do this well at all*) to 7 (*I can do this very well*).
- **Knowledge of Coping Skills.** Coping skills will be measured using the Brief COPE (Carver, 1997), which is a multidimensional scale that assesses a range of adaptive and maladaptive coping strategies. There are 28 items that measure problem-focused coping, emotion-focused coping, and avoidant coping strategies. Though the original Brief COPE is intended for adults, researchers have adapted it for use with adolescents (e.g., Yuan et al., 2017; Yusoff, 2011). The authors of the scale report that most alphas were above .60, and exploratory factor analysis supported the hypothesized factor structure.

**1.4 Describe what data will be collected during the study and how that data will be obtained.**

Data will be collected through several surveys both pre- and post-test using electronic surveys via qualtrics. The measures are described above.

**2.0 Study Timelines**

**2.1 Describe:**

- *The duration of an individual subject's participation in the study.*

*10 weeks. One week of data collection before and after the 8 week intervention.*

- *The duration anticipated to enroll all study subjects.*

*Enrollment for the foundation-funded project will occur during September 2023-April 2024.*

*Enrollment for the NIH-funded project will occur during August 2024-May 2025.*

**3.0 Inclusion and Exclusion Criteria**

**3.1 Describe how individuals will be screened for eligibility.**

Participants will be sixth-, seventh-, and eighth-grade students who have experienced peer victimization.

**3.2 Describe the criteria that define who will be included or excluded in your final study sample.**

No restrictions will be placed on gender or race, though attempts will be made to balance the groups in relation to these demographic characteristics (e.g., avoid groups that have one or two girls and six boys).

To be eligible for the study, the students must 1) be a middle school or high school student (via parent report), 2) have access to a computer with webcam and a private space for each meeting (via parent report), 3) and report distress from victimization by peers that has occurred in the past month

**3.3 Indicate specifically whether you will include or exclude each of the following special populations: (You may not include members of the above populations as subjects in your research unless you indicate this in your inclusion criteria.)**

Individuals who are not yet adults (infants, children, teenagers) will be included in this study.

## 4.0 Recruitment Methods

### 4.1 *Describe when, where, and how potential subjects will be recruited.*

The intervention will be delivered virtually via a HIPAA-compliant Zoom meeting. Since the intervention will not occur at a single school and everything will be completed through virtual meetings, youth can be recruited from anywhere.

*Describe the source of subjects.*

Via advertisements in the outlets mentioned above (local social media groups) or through contacts with local middle schools.

Participants will receive a \$75 gift card if they complete the pre-test, 8 week intervention, and post-test. They must be present for at least 6 of the 8 sessions. They will receive an additional \$25 gift card if they also complete the post-intervention focus group. Partial completion will not be compensated, nor will early withdrawal from the study.

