### 5.3 *Describe procedures that will be followed when subjects withdraw from the research, including partial withdrawal from procedures with continued data collection.*

If subjects wish to withdraw, their data will be deleted and they will not be included in the planned analysis.

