## **8.0 Data Management and Confidentiality**

### *8.1 Describe the data analysis plan, including any statistical procedures or power analysis.*

An initial indication of changes in the outcome variables will be explored. A repeated measures ANOVA will be used to assess change in pre- and post- outcome measures. The small sample size may limit the power to detect statistically significant differences (Thompson, 1996; Valentine & Cooper, 2003); thus, effect sizes will also be calculated. Based on a large meta-analysis of over 800 meta-analyses in education, Hattie (2009) categorized a small effect as .20, medium as .40, and large effect as .60. If there is missing data (e.g., a participant dropped out), scores will be deleted list-wise.

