### *8.2 Describe any procedures that will be used for quality control of collected data.*

Missing data is the most salient issue with quality of the data. Participants will be asked to complete all questions on the surveys. To reduce attrition in the intervention over time and missing data in the pre- and post-intervention surveys, several strategies will be employed. First, to incentive attendance, compensation will be provided to participants that attend at least 6 intervention sessions and complete the post-intervention surveys. This will be made clear in the consent and assent documents. Second, reminders will be sent the day before each session to remind the participant and their parent about the day and time of the session. Third, to overcome barriers to access, the intervention will be scheduled at a time that is deemed appropriate by the school based on student schedules and the academic calendar. These strategies are in line with previous research on attrition and treatment adherence (Nock & Ferriter, 2005; Snell-Johnson et al., 2004).

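### Payment and the post-test request both hinge on attendance, so low attenders in the treated arm may have no outcome; this risks attrition bias, probably in favour of the intervention

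*Protocol*

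**What the plan says.** **Payment.** Protocol section 4.1 offers a single 75-dollar "gift card if they complete the pre-test, 8 week intervention, and post-test". It adds the attendance condition "They must be present for at least 6 of the 8 sessions" and rules out part payment: "Partial completion will not be compensated, nor will early withdrawal from the study". A further 25 dollars is for the focus group.

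**Stated purpose.** Section 8.2 lists the payment among its measures against attrition and missing surveys, with the same joint condition: "compensation will be provided to participants that attend at least 6 intervention sessions and complete the post-intervention surveys". The other measures are session reminders and convenient scheduling.

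**Who is asked.** Section 1.2 says: "Participants completing the intervention will be asked to complete the post-test surveys". It does not define completing; the only attendance threshold in the protocol is the one for payment.

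**What happens to missing outcomes.** Section 8.1 says: "If there is missing data (e.g., a participant dropped out), scores will be deleted list-wise". Section 5.1 gives not completing the survey as a ground for withdrawal, and section 5.3 says: "If subjects wish to withdraw, their data will be deleted and they will not be included in the planned analysis".

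**Comparison.** Under section 1.1 the waitlist group starts only when the experimental group has finished. The SAP compares treatment with control at time 1 and time 2. It reports missing data on social-support items only.

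**The concern.** A retention payment should give participants a reason to return the outcome survey whatever their engagement with the treatment. Here the payment is lost at the third missed session. From then on it cannot do what section 8.2 wants of it, and this happens among the youths whose surveys are most likely to go missing. Section 1.2 compounds the problem, because on its wording these youths may never be asked.

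The mechanism sits in one arm. Before time 2 only treated youths have sessions to miss, so only in that arm can attendance decide whether an outcome exists. If poor attenders also improve less, the treated mean is taken over a favourable subset and the group-by-time contrast moves towards benefit. Section 8.1 expects low power and turns to effect sizes, with 0.20 as its benchmark for a small effect. A shift of around 0.1 SD is therefore not trivial for the result the study means to report.

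**Working it through.** The documents give no dropout, attendance or sample-size figure, so there is no planned figure to reproduce. What follows is illustrative.

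**Inputs from the documents.** Group size 6-7 (section 1.2); payment threshold 6 of 8 sessions (section 4.1); list-wise deletion (section 8.1).

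**Assumptions.** The arm is one group of 6 or 7. One youth, the poorest attender, is lost. Attendance and improvement are roughly bivariate normal with correlation r = 0.3-0.5.

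**Step 1: threshold.** 8 - 6 = 2 absences are allowed, so the third absence forfeits the whole card.

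**Step 2: one lost youth.** The expected minimum of n standard normal values is -1.352 for n = 7 and -1.267 for n = 6. The values sum to zero in expectation, so the mean attendance of those who remain is:

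- n = 7: 1.352/6 = +0.225 SD
- n = 6: 1.267/5 = +0.253 SD

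Multiplying by r gives the shift in the arm's mean change:

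| n | r = 0.3 | r = 0.5 |
|---|---|---|
| 7 | 0.068 | 0.113 |
| 6 | 0.076 | 0.127 |

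The range is about 0.07-0.13 SD. The uncorrelated-scale values of 0.225 and 0.253 SD would apply only if the lost youth were exactly the least improved (r = 1), which is a worst case.

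**Step 3: cross-check with the complete-case identity.** Shift = q x d, where q is the share of the arm lost and d is the mean improvement of those retained minus that of those lost. For n = 7, q = 1/7 = 0.143 and d = r x (0.225 + 1.352) = r x 1.577, which is 0.47-0.79. Then q x d = 0.07-0.11, in agreement with step 2.

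**Step 4: more than one lost.** With 2 of 7 lost, q = 0.286. The shift is +0.06 SD for d = 0.2, +0.14 for d = 0.5 and +0.23 for d = 0.8. It is 0 for d = 0, and -0.14 for d = -0.5 (low attenders doing better).

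**Step 5: both arms.** Net bias = qT x dT - qC x dC. With d = 0.5 in each arm:

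| Lost, treated | Lost, waitlist | Net bias (SD) |
|---|---|---|
| 2/7 | 0 | +0.14 |
| 2/7 | 2/7 | 0 |
| 1/7 | 2/7 | -0.07 |

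**Step 6: larger arm.** The step 2 method for one lost youth gives 0.04-0.07 SD with 14 per arm and 0.02-0.04 SD with 28.

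**Step 7: precision.** With 7 per arm the standard error of a standardised difference is sqrt(2/7) = 0.53. The one-youth shift at n = 7 is at most 0.113/0.53, about one fifth of that.

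**The case against.** Several objections have force.

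- **Low attenders are not excluded by rule.** A reader might infer that missing a third session means deletion. The documents do not say so. Section 5.1 withdraws nobody for poor attendance, and section 8.1 acts only on missing data. A low attender who returns the post-test stays in. What is lost is the financial reason to return it, not every reason. This stands.
- **Waitlist payment is unstated, not denied.** A reader might infer that control youths are unpaid for their time-2 survey. The documents do not say how the card applies to that survey. Waitlist youths go on to receive the intervention and can presumably earn the card; if the time-2 survey serves as their pre-test, it would count towards it. This stands.
- **A group of 6-7 may not be the whole arm.** Section 3.2 speaks of groups, section 2.1 gives two enrolment periods, and total N is not stated. The illustration shrinks in a larger arm, as step 6 shows. This stands.
- **The SAP reports no missing outcomes beyond social-support items.** On its face, no post-test in the analysed data was lost this way. But the SAP does not say whether dropouts had been removed beforehand. Sections 5.1 and 5.3 together would remove a youth who did not complete the survey, and the remaining data would then look complete. The statement settles the matter neither way.
- **Other retention measures exist.** Reminders and scheduling support attendance at sessions. Neither is described as a way of obtaining a post-test from someone who has stopped attending.

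**Conclusion.** The point holds as a risk of attrition bias. The payment rule, the wording of the post-test request and list-wise deletion are all in the text. Together they let attendance decide whether a treated youth contributes an outcome.

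The stronger statement that the effect is biased upward is tempting but not supported. It needs low attenders to improve less and the loss not to be matched in the waitlist arm, and the documents show neither. The upward direction is the more likely one, since only the treated arm has sessions to miss before time 2. Steps 4 and 5 show that the net bias can also be zero or negative.

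The illustrative size is 0.07-0.13 SD for one lost youth. It rests on an arm of 6-7, loss of the poorest attender, an assumed correlation of 0.3-0.5 and no waitlist loss. That is small beside the sampling error, but it is systematic and can be largely prevented. This is a cheap improvement to the design, not a fault that invalidates the trial.

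**What to change.** 1. **Section 1.2:** request the post-test from all randomised youths in both arms, whatever their attendance, unless consent or assent is withdrawn.
2. **Sections 4.1 and 8.2:** tie a stated part of the existing 75-dollar card to the pre- and post-test surveys regardless of attendance, in both arms, and the rest to attending at least 6 sessions. Say which survey counts as the waitlist arm's time-2 measurement.
3. **Section 8.1 and the SAP:** state that low attenders with a post-test are analysed in their assigned arm, and report the numbers randomised and analysed per arm.

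If every post-test is obtained and analysed, q = 0 in both arms and this bias term is zero. No stated sample-size or power figure changes, because there is none.

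The cost is revised consent and protocol wording, the survey part of the card for the few low attenders, and a slightly weaker incentive to attend. The change helps only participants not yet past their post-test. Foundation-funded enrolment was planned to end in April 2024 and NIH-funded enrolment in May 2025 (section 2.1). The SAP, dated October 2024, already describes its analyses in the past tense. For anyone already past the post-test, only item 3 is still useful.

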## 5.0 Withdrawal of Subjects

### 5.1 *Describe anticipated circumstances under which subjects will be withdrawn from the research without their consent.*

Subjects will not be withdrawn from the study unless they choose to not complete the survey during the data collection process. Participants may be asked to discontinue if they are too distressed by the topic that it would not be healthy for them to continue.

### 5.2 *Describe any procedures for orderly termination.*

If subjects are terminated, their data will be deleted and they will not be included in the planned analysis.

### 5.3 *Describe procedures that will be followed when subjects withdraw from the research, including partial withdrawal from procedures with continued data collection.*

If subjects wish to withdraw, their data will be deleted and they will not be included in the planned analysis.

6.2 *If information about the study's actual purpose will not be completely or accurately described to study subjects, or in any way be withheld, obscured, masked, or blinded from study subjects (e.g., you want to avoid participation bias or priming prospective subjects), you are required to describe here that you will: (a) as part of the consent process provide subjects with a statement to the effect that subjects may not be made aware of some features about the study, such as its exact purpose, study questions and materials, or subjects' responses that you would like to collect, and that subjects will be provided with additional information about the study at the end of their participation or at any time they withdraw, (b) debrief subjects at the end of their participation or at any time they withdraw, and (c) provide the IRB with a copy of all materials that will be used to debrief subjects.*

No information is withheld, obscured, masked, or blinded from subjects.

6.3 *If applicable, indicate which procedures may have risks to the subjects that are currently unforeseeable.*

There is a chance that engaging in the online sessions could risk privacy if the participant does not have a private place to log in to their sessions. Using a private room without anyone else in the room will be emphasized to both parents and participants

## 7.0 Potential Benefits to Subjects

7.1 *Describe the potential benefits that individual subjects may experience from taking part in the research. Include as may be useful for the IRB's consideration, the probability, magnitude, and duration of the potential benefits.*

The goal of the study is to potentially alleviate some of the distress the participants are experiencing. Participants will learn a variety of skills for coping with emotional difficulties, as well as strategies for how to protect themselves in the future. Through learning these skills, the hope is for participants to thrive academically and socially despite the challenging circumstances they have faced.

7.2 *Indicate if there is no direct benefit. Do not include benefits to society or others. Also, payment to research subjects for participation in studies is*

*not considered a benefit so do not list payment to research subjects in this section; if a recruitment incentive will be offered, described this in section 13 under Recruitment Methods.*

The direct benefit is described in section 16.1. The goals of the intervention is for the subjects to feel reduced distress and learn skills to dealing with future victimization.

## **8.0 Data Management and Confidentiality**

### *8.1 Describe the data analysis plan, including any statistical procedures or power analysis.*

An initial indication of changes in the outcome variables will be explored. A repeated measures ANOVA will be used to assess change in pre- and post- outcome measures. The small sample size may limit the power to detect statistically significant differences (Thompson, 1996; Valentine & Cooper, 2003); thus, effect sizes will also be calculated. Based on a large meta-analysis of over 800 meta-analyses in education, Hattie (2009) categorized a small effect as .20, medium as .40, and large effect as .60. If there is missing data (e.g., a participant dropped out), scores will be deleted list-wise.

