## 9.0 Provisions to Monitor the Data to Ensure the Safety of Subjects

### 9.1 Describe:

- *The plan to periodically evaluate the data collected regarding both harms and benefits to determine whether subjects remain safe. The plan might include establishing a data monitoring committee and a plan for reporting data monitoring committee findings to the IRB and the sponsor.*

A data safety and monitoring plan was developed to ensure that appropriate protocols were in place since children are the primary target population. [name] (PI) will be responsible for all aspects of the project, including design, data collection, and use of data. [name] will be responsible for monitoring data to ensure the safety of participants. Data will be collected at the beginning and end of the study, approximately 10 weeks between data collections. All data will be collected via Qualtrics that only the PI will have access to. Responses will be viewed within 48 hours of survey completion to examine for any distress the participant may express. A descriptive analysis will be conducted as the data come on. At the end of the experimental group, statistical tests will be conducted to ensure that the intervention did not cause excessive distress, particularly we will examine if the internalizing distress score shows an increase of distress more than 10 points on the Tscore scale. If more than 5 participants show an increase in their Tscore for internalizing distress, the waitlist control group will not begin until the team has had a chance to interview the participants to determine if it was the intervention that caused the increase in distress. Unanticipated problems involving risks to participants will be promptly reported to the IRB. The PI will review the progress of the project and data being collected to ensure that potential adverse effects are identified, and if they occur it will be

reported to the IRB. Any action recommended by the IRB to the PI will be implemented immediately.

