Official Title: IVY: Intervention for Victimized Youth

NCT Number: NCT06631274

Document Date: October 18, 2024

Analytic Plan

Analytic Plan

Statistical analyses included three steps. First, missing data occurred only on items measuring social support. Little's test was used to examine the tenability of the assumption of missing completely at random. Second, the mean scores across items in each scale/subscale were computed to represent each intermediate and distal outcome. Third, a series of one-way repeated measures ANOVAs was conducted to examine the impact of intervention, in which participation in the intervention (treatment vs. control) was used as the between-subject factor and time points (time 1 and time 2) was used as the within-subject factor. In addition to significance test for main effect of group, main effect of time, and the interaction effect between time and group, Hedges' g was computed to indicate effect size, where values of 0.2, 0.5, and 0.8 indicate a small, medium, and large effect respectively.

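### Hedges' g is offered as the answer to low power but is read only by size labels, with no confidence interval and no stated contrast or standardising SD

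*Protocol*

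**What the plan says.** Protocol section 8.1 plans a repeated measures ANOVA and concedes a limit: "The small sample size may limit the power to detect statistically significant differences". Its response is the next clause: "thus, effect sizes will also be calculated". It does not name the effect-size statistic. It takes verbal categories from a review of education meta-analyses that "categorized a small effect as .20, medium as .40, and large effect as .60".

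The SAP's Analytic Plan fits treatment versus control as the between-subject factor, and "time points (time 1 and time 2) was used as the within-subject factor". It introduces the effect size with the words "In addition to significance test for main effect of group, main effect of time, and the interaction effect between time and group", and says that Hedges' g "was computed to indicate effect size, where values of 0.2, 0.5, and 0.8 indicate a small, medium, and large effect respectively".

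That is all either document says about effect sizes. There is no confidence interval, standard error or other measure of precision. Three effects are tested, and g is not tied to any of them. No SD is named as its denominator.

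**The concern.** The effect size is there because the tests may be underpowered, so if the tests are inconclusive the reader will turn to g. But g is estimated from the same few participants. Without an interval, the addition to the p-value is one word attached to an imprecise number. A result called *medium* could equally fit almost no benefit, or a very large one, and the report would not show it.

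The definition of g is the second gap. The ANOVA is meant to assess the impact of the intervention, so a between-group g is the natural reading. Two choices remain open: the difference at time 2 or the difference in change, and the raw-score SD or the SD of change scores. Each can alter the value and its label on the same data.

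**Working it through.** **Inputs.** Neither document gives a total N, N per arm, an SD, a pre-post correlation or a target effect, so there is no figure of the plan's own to reproduce. The only size given is in Protocol section 1.2: "The goal is to enroll 6-7 students in the group". That may describe one therapy group rather than a trial arm. The safety trigger in section 9.1 ("If more than 5 participants show an increase in their Tscore for internalizing distress") would need at least 6 participants, which is all or nearly all of an arm of 6 or 7. I therefore show 6, 7, 14 and 30 per arm.

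Assumptions: equal arms, independent participants, equal SD at both times, and pre-post correlation r where needed.

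**Step 1: interval when g uses the SD of the compared score.** With n per arm:

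- df = 2n - 2
- small-sample factor J = 1 - 3/(4df - 1)
- t = (g/J)/√(2/n)
- find the noncentrality values that place the observed t at the 97.5th and 2.5th percentiles, then multiply by √(2/n) × J.

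For n = 7 and g = 0.5: df = 12; J = 1 - 3/47 = 0.936; √(2/7) = 0.5345; t = 0.534/0.5345 = 1.00. The noncentrality limits are -1.02 and 2.98. Multiplying by 0.5345 × 0.936 = 0.500 gives -0.51 to 1.49.

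**Step 2: interval when g is the difference in mean change over the raw SD.** The SD of change is raw SD × √(2(1 - r)), so √(2/n) is replaced by √(2(1 - r)) × √(2/n). This treats r as known, so the results are approximate.

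| n per arm | 95% CI for g = 0.5, SD of compared score | Width | 95% CI for g = 0.5, change over raw SD, r = 0.8 |
|---|---|---|---|
| 6 | -0.58 to 1.55 | 2.13 | -0.21 to 1.18 |
| 7 | -0.51 to 1.49 | 2.00 | -0.16 to 1.14 |
| 14 | -0.24 to 1.23 | 1.47 | 0.02 to 0.97 |
| 30 | -0.01 to 1.01 | 1.02 | 0.17 to 0.83 |

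All eight intervals run from below 0.2 to above 0.8 on the SAP's scale. At r = 0.9 the interval still does so with 14 per arm (0.15 to 0.84), but with 30 it is 0.26 to 0.74 and does not. The interval for g = 0.5 first fits inside 0.2 to 0.8 at 88 per arm with the SD of the compared score, and at 37 per arm with the raw SD and r = 0.8.

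**Step 3: effect of the standardiser.** Take a between-group difference in change of 0.5 raw SD, before the factor J. Over the raw SD it is 0.50. Over the change SD it is 0.5/√(2(1 - r)):

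| r (assumed) | 0.5 | 0.7 | 0.8 | 0.9 |
|---|---|---|---|---|
| g over change SD | 0.50 | 0.65 | 0.79 | 1.12 |

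The same data can therefore sit at the SAP's *medium* value or go past its *large* value.

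**Step 4: effect of the contrast.** The difference in change equals the time-2 difference minus the time-1 difference. By chance alone, the time-1 difference has a standard error of √(2/n) raw SDs: √(2/7) = 0.53 at 7 per arm and √(2/30) = 0.26 at 30. In arms that small the two contrasts can easily differ by an amount that changes the label.

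**Step 5: labels.** Read as lower cut-points, the protocol's 0.20/0.40/0.60 and the SAP's 0.2/0.5/0.8 disagree for values from 0.40 to just under 0.50 and from 0.60 to just under 0.80. No estimate or test changes.

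**The case against.** The strongest reply is that this is a reporting gap in an exploratory study. Section 8.1 seeks only a first indication of change and is open about power. Nothing says that intervals will be withheld, and adding one changes no test, estimate or sample. All of that is true. But exploratory work rests on estimation more than on tests, and the SAP does state a rule for reading g: the labels. Replacing that rule with an interval is a real improvement.

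It is also fair that Hedges' g conventionally implies a pooled SD with a small-sample correction, and that the SAP's purpose points to a between-group comparison. This removes the within-group reading. It also makes it unlikely that g belongs to the group main effect, although the text does not exclude that. It does not settle time 2 versus change, or raw SD versus change SD.

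A reader might infer four stronger things that the documents do not support:

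- *Each arm has 6 or 7 participants.* The wording may describe one therapy group, and the safety trigger fits a larger arm better.
- *An interval could not be obtained.* It can always be computed from the data at analysis, when N is known. The plan simply does not commit to one.
- *Values of g in the bands where the labels disagree could not be significant.* That depends on N, the standardiser and r, none of which is given, and there is no clean threshold.
- *The label mismatch affects conclusions in its own right.* It changes words only.

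**Conclusion.** The point holds as a gap in how the effect size is defined and interpreted. Section 8.1 presents effect sizes as the response to limited power, and the SAP then reads g by labels alone, without an interval, a stated contrast or a named SD.

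On the SD of the compared score, an observed g of 0.5 has a 95% interval about 2 units wide at 6 to 7 per arm and about 1 unit wide at 30, reaching from below *small* to above *large* throughout. The choice of denominator alone moves the same result from 0.50 to 0.79 at r = 0.8.

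These sizes rest on assumed N, equal arms, independence and r. Delivery in small therapy groups may make participants within a group alike, and positive correlation of that kind would generally add to the uncertainty. In the other direction, a raw-SD denominator with high r narrows the intervals, so it is not true that every plausible design leaves all the labels open. The change is worth making. The differing cut-offs are a consistency edit and add no weight.

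**What to change.** In the SAP, add wording to this effect: *For each outcome, Hedges' g is the between-group difference in mean change from time 1 to time 2, divided by [one named SD] with small-sample correction. Each g is reported with a 95% confidence interval, and interpretation rests on the interval rather than on the size label.* This contrast is the time-by-group interaction that the SAP already tests.

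The interval method must match the SD chosen. With the change SD, noncentral-t inversion applies directly. With a raw SD, the method must allow for the pre-post correlation and for its estimation.

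As a consistency edit only, have Protocol section 8.1 refer to the SAP's cut-offs instead of giving a second set.

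The cost is one or two sentences in the SAP, one in section 8.1 and one column in the results table. No new data are needed. The real price is that wide intervals will make the results look less favourable than a bare label would.
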